### **3.3.7 Handling of Unscheduled Visits**

#### **3.3.7.1 For Tables, Listings and Figures**

Subject data listings will include data obtained from unscheduled visits chronologically.

By-visit summaries will not include unscheduled visits. Across-visits summaries, eg, summaries of occurrences will include unscheduled assessments.

### **3.3.7.2 For Pharmacokinetic Analysis**

In case a serum PK sample is drawn at an unscheduled visit, PK analysis will include the unscheduled concentrations.

### **3.3.8 Multiplicity/Multiple Comparisons**

No hypotheses are planned to be formally tested using inferential statistics in this study so multiplicity is not a concern.

### **3.3.9 Handling of Protocol Deviations in Study Analysis**

Protocol deviations will be captured and presented as described in Section 4.1.3. The protocol deviations and their categorization to “important” or “non-important” are pre-defined as far as possible before inclusion of the first participant. Final categorization of protocol deviations and actions for analysis will be done continuously during the study but finalized prior to the final analysis and any interim analysis.

For details on definition of protocol deviations, please refer to the study-specific Protocol Deviation Specification.

## **4 STATISTICAL ANALYSIS**

This section provides information on definitions, derivation and analysis/data presentation per domain.

### **4.1 Study Population**

The domain study population covers subject disposition, analysis sets, protocol deviations, demographics, baseline characteristics, medical history, prior and concomitant medication, and study drug compliance.

#### **4.1.1 Analysis Sets**

##### **4.1.1.1 Definitions and Derivations**

Before database lock for the final or interim analysis, protocol deviation categories and the analyses populations will be produced for review. An analysis set classification meeting will be arranged to discuss the outputs and to decide which participants and/or participant data will be excluded from certain analyses. Decisions made regarding the exclusion of participants and/or participant data from analyses will be documented and approved by the sponsor.

**Table 1: Analysis sets**

Population/Analysis Set	Description
Screened Population Set (SPS)	All participants who signed the ICF. Unless otherwise stated, this set will be used for the presentation of disposition data.
Full Analysis Set (FAS)	All participants who received the IMP, irrespective of their protocol adherence and continued participation in the study. Participants who withdraw consent or assent to participate in the study will be included up to the date of their study termination.
Modified Full Analysis Set (mFAS)	All participants who are in the FAS, excluding participants who were assigned to Cohort 1 by rapid COVID-19 test, but have a positive confirmatory test.
Safety Analysis Set (SAF)	All participants who have received IMP.
PK Analysis Set (PKS)	All participants who received AZD7442 and from whom PK blood samples are assumed not to be affected by factors such as protocol violations, and who had at least one quantifiable serum PK observation post-dose, will be included in the PK analysis dataset.
AZD1061 ADA Evaluable Analysis Set (ADS1)	A participant is AZD1061 ADA evaluable if in the SAF and having a non-missing baseline AZD1061 ADA result and at least one non-missing post-baseline AZD1061 ADA result.
AZD8895 ADA Evaluable Analysis Set (ADS2)	A participant is AZD8895 ADA evaluable if in the SAF and having a non-missing baseline AZD8895 ADA result and at least one non-missing post-baseline AZD8895 ADA result.
AZD7442 ADA Evaluable Analysis Set (ADS3)	All participants who are AZD8895 ADA evaluable and/or AZD1061 ADA evaluable.
SARS-CoV-2 nAb Evaluable Analysis Set (SES)	All participants in the Safety Analysis Set from whom blood samples were assumed not to be affected by factors such as protocol violations, and who had at least one quantifiable serum titer observation post dose.

Generally, all listings will be prepared based on the SAF unless otherwise stated.  
Disposition data will be listed for the SPS.

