^c Perform 15 minutes (± 5 minutes) after the IMP injection is complete.

^d Collection of urine samples from participants who are unable to provide urine samples is not mandatory provided that a reasonable attempt has been made to collect the samples.

^e Baseline sample, not a screening sample; results not needed prior to dosing.

^f All participants will have sample collected for SARS-CoV-2 RT-PCR on Day 1. Only Cohorts 2 and 3 (treatment arms) will have a sample collected for quantitative RT-PCR on Day 1 and Day 8. For RT-PCR, the central laboratory should be used. For participants in Cohort 1 that have COVID-19 qualifying symptoms (Table 13) at any time during the study, an unscheduled sample will be collected for SARS-CoV-2 RT-PCR to confirm the participant is SARS-CoV-2 positive (Section 8.1.1).

^g For participants who receive AZD7442 via an IV infusion, a serum sample should be taken at the end of the infusion (and from the opposite side to the one used for the infusion).

^h All participants will be monitored on site for general safety, including injection/infusion site reactions and other hypersensitivity reactions, for at least one hour after IMP administration (Section 8.3.1).

ⁱ All participants will be contacted weekly starting from the time of IMP administration. During weekly contacts the Investigator will enquire about AEs, SAEs, MAAEs, and AESIs as well as any COVID-19 symptoms from the past 7 days.

Where necessary, the visit windows in the SoA can be used to collect samples across a number of days. When sample collection occurs over ≥ 2 days for a given study visit, participants are required to visit the site at least once per study visit. If practical, additional sample collection can take place at home visits as long as the samples are obtained per protocol by qualified personnel.

ADA, anti-drug antibody; AE, adverse event; AESI, adverse event of special interest; COVID-19, Coronavirus disease-2019; ECG, electrocardiogram; FU, follow-up; IMP, investigational medicinal product; IV, intravenous; MAAE, medically attended adverse event; NA, not applicable; PK, pharmacokinetic; RT-PCR, reverse transcriptase polymerase chain reaction; SAE, serious adverse event; SARS-CoV-2, severe acute respiratory syndrome coronavirus 2; SoA, schedule of activities.

Table 3 Schedule of Activities: Treatment and Follow-up Period for Participants Other Than Neonates – Main Study

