4 STUDY DESIGN

4.1 Overall Design

This is a Phase I, open-label, uncontrolled, multicountry, multicenter, single dose study to evaluate the PK, PD, safety, and tolerability of AZD7442 administered IM or IV in pediatric participants aged \geq 29 weeks GA (infants born between gestational age of 29 weeks to full

term) to < 18 years. Up to 3 cohorts of participants will be enrolled based on the adult indication and dose: 1) participants who are SARS-CoV-2 negative at screening and have not knowingly been exposed to a SARS-CoV-2 positive individual (pre-exposure prophylaxis); 2) participants who are SARS-CoV-2 RT-PCR positive at screening and have mild to moderate COVID-19; and 3) participants who are SARS-CoV-2 positive at screening and have severe COVID-19. Both Cohort 1 and Cohort 2 are required to be at increased risk of developing severe COVID-19. Recruitment will start with Cohort 1; Cohorts 2 and 3 will be added if the indications are progressed in adults. If recruitment in a cohort is not initiated, the minimum number of participants in the other cohort(s) will be increased such that there is a minimum of 6 participants receiving IV administration and a minimum of 6 participants receiving IM administration of the IMP in each of the four main age categories. Approximately 33 sites will participate in this study.

To facilitate recruitment, participants will be assigned to a cohort and receive treatment based on the results of a documented RT-PCR test taken \leq 3 days before Day 1 (if available) or a SARS-CoV-2 rapid antigen test at screening. A sample will also be taken on Day 1 for a pre-dose SARS-CoV-2 RT-PCR test to be conducted at the central laboratory (baseline).

Participants will continue in their assigned cohort even if the Day 1 pre-dose SARS-CoV-2 RT-PCR test does not confirm the initial screening test results. Approximately 120 participants will be enrolled to ensure a minimum of 100 evaluable participants. If necessary, recruitment will be increased to replace participants who withdraw from the study.

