5.1 Inclusion Criteria

Participants are eligible to be included in the study only if all the following criteria apply:

Age and Weight

- 1 Participant must be aged \geq 29 weeks GA to $<$ 18 years of age at the time of signing the informed consent (see Appendix A 3 for procedures around informed consent).
- 2 Participant must weigh a minimum of 1.5 kg.

Type of Participant and Disease Characteristics

COHORT 1: Participants who do not have COVID-19 and have not knowingly been exposed to a SARS-CoV-2 positive individual (pre-exposure prophylaxis):

- 3 At increased risk of severe COVID-19 for any of the following reasons:
 - (a) Immunocompromised state
 - (b) One or more comorbid conditions that increase the risk of severe COVID-19, eg, cardiovascular disease, including heart disease since birth, malignancy, chronic kidney disease, and genetic, neurologic, or metabolic conditions.
- 4 Medically stable defined as disease not requiring significant change in therapy or hospitalization for worsening disease during the one month prior to enrollment, with no acute change in condition at the time of study enrollment as judged by the Investigator.
- 5 Documented negative SARS-CoV-2 RT-PCR test collected \leq 3 days prior to Day 1 or a negative rapid SARS-CoV-2 antigen test at screening.
- 6 Prior to enrollment, participants must not have had COVID-19 symptoms (Table 13) within 10 days of dosing.

7 Increased risk for SARS-CoV-2 infection, defined as those whose locations or circumstances put them at appreciable risk of exposure to SARS-CoV-2 and COVID-19, based on available risk assessment at time of enrollment.

COHORT 2: Participants with COVID-19 and mild to moderate symptoms (treatment):

8 At increased risk of severe COVID-19 for any of the following reasons:

- (a) Immunocompromised state
- (b) One or more comorbid conditions that increase the risk of severe COVID-19 (see list in 3[b])

9 Medically stable defined as disease not requiring significant change in therapy or hospitalization for worsening disease during the one month prior to enrollment, with no acute change in condition at the time of study enrollment as judged by the Investigator.

10 Documented positive SARS-CoV-2 RT-PCR test collected \leq 3 days prior to Day 1 or a positive rapid SARS-CoV-2 antigen test at screening.

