### **Cohorts**

Cohort 1: Pediatric participants who are SARS-CoV-2 negative at baseline

Cohort 2: Pediatric participants who are SARS-CoV-2 positive at baseline and have mild to moderate COVID-19

Cohort 3: Pediatric participants who are SARS-CoV-2 positive at baseline and have severe COVID-19

In case a participant is assigned to Cohort 1 via a negative rapid COVID-19 test at screening, but the confirmatory test result is positive, the participant stays assigned to Cohort 1.

Cohort 3 will be empty due to discontinuation of enrolment. No change to enrolment in Cohort 1 and 2 was made.

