**Table 2: Analysis Endpoints**

Objectives	Endpoints	Analysis Set
Primary		
To evaluate the serum concentrations of AZD7442 after a single IM or IV dose in pediatric participants	Serum concentrations of AZD7442 at specified time points during the one-year study period when administered as a single IM or IV dose  Serum PK parameters (if data permits): Cmax, tmax, t1/2, AUC0-last , AUC0-inf , tlast, %AUCext, and: 

• for IM: CL/F, and Vz/F

• for IV: CL, and Vss

 Model-derived predicted serum AZD7442 concentrations, Cmax and AUC0-inf	PKS
To evaluate the safety and tolerability of AZD7442 after a single IM or IV dose in pediatric participants	TEAEs, SAEs, and AESIs (including anaphylaxis, injection/infusion site reactions, MIS-C).  Safety laboratory parameters (hematology, clinical chemistry, coagulation, and urinalysis); 12 lead safety ECG; vital signs (BP, pulse rate, tympanic membrane temperature, and respiratory rate), and physical examination.	SAF
Secondary – All Cohorts		

Objectives	Endpoints	Analysis Set
To evaluate the PD of AZD7442 after a single IM or IV dose	Titer of SARS-CoV-2 neutralizing antibodies	SES
To evaluate the immunogenicity profile of AZD7442	Incidence of ADA and nAb to AZD7442 in serum	ADS1/2/3
Secondary – Cohort 1 (Prophylaxis)		
To evaluate the incidence of SARS-CoV-2 infections with or without COVID-19 symptoms after a single IM or IV dose of AZD7442 in pediatric participants	Incidence of SARS-CoV-2 infections with and without COVID-19 symptoms	SAF, mFAS
Secondary – Cohort 2 and Cohort 3 (Treatment)		
To quantify SARS-CoV-2 viral loads after a single IM or IV dose of AZD7442 in pediatric participants	Change from baseline to Day 8 in viral load as measured by qRT-PCR.	SAF
To evaluate the proportion of participants with progression of COVID-19 after a single IM or IV dose of AZD7442 in pediatric participants	Proportion of participants with progression of COVID-19 through Day 29	SAF
To evaluate COVID-19 related death through 90 days after a single IM or IV dose of AZD7442 in pediatric participants	The incidence of COVID-19-related death occurring after dosing with IMP up to study day 90	SAF
Secondary – Cohort 3 (Severe COVID-19)		

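### The mFAS removes Cohort 1 children already infected at dosing only if they entered on a rapid test; those who entered on an earlier negative RT-PCR stay in the infection-incidence sensitivity analysis

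*SAP*

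**What the plan says.** - **Entry to Cohort 1.** Protocol 5.1, criterion 5, accepts either of two tests: "Documented negative SARS-CoV-2 RT-PCR test collected" no more than 3 days before Day 1, "or a negative rapid SARS-CoV-2 antigen test at screening". A footnote to protocol Table 1 adds that the rapid test is done when no documented RT-PCR is available.
- **Day 1 test.** Every child gives a pre-dose sample for central RT-PCR. The footnotes to protocol Tables 2 and 3 describe it thus: "Baseline sample, not a screening sample; results not needed prior to dosing". Protocol 4.1 then says: "Participants will continue in their assigned cohort even if the Day 1 pre-dose SARS-CoV-2 RT-PCR test does not confirm the initial screening test results". That sentence covers both entry tests and all cohorts.
- **SAP rule on discordance.** SAP 3.2 (Cohorts) covers one situation: "In case a participant is assigned to Cohort 1 via a negative rapid COVID-19 test at screening, but the confirmatory test result is positive". Such a child remains in Cohort 1. SAP Table 1 then defines the mFAS as the FAS "excluding participants who were assigned to Cohort 1 by rapid COVID-19 test, but have a positive confirmatory test". The SAP does not say which test is the confirmatory one.
- **Use of the mFAS.** SAP Table 2 lists it for one endpoint, Cohort 1 infection incidence, next to the SAF. SAP 4.2.4 carries out the repeat.

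**The concern.** The mFAS is useful only if it separates infections acquired after dosing from those already present. The protocol allows the Day 1 result to contradict either entry test, but the SAP acts on the contradiction only when the entry test was a rapid test. Which test a child had depends on whether a recent RT-PCR happened to be on file, and the SAP gives no reason to treat the two groups differently.

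The sensitivity repeat could therefore still contain children who were positive before they received AZD7442. If they are counted as cases, an infection present at dosing appears as a failure of prophylaxis in the very analysis meant to exclude it.

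**Working it through.** **Step 1. Who is removed.** The four combinations for a Cohort 1 child, using SAP Table 1 as written and taking the confirmatory test to be the Day 1 central RT-PCR:

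| Entry test (negative) | Day 1 pre-dose central RT-PCR | In SAF | In mFAS |
|---|---|---|---|
| Rapid antigen | Negative | Yes | Yes |
| Rapid antigen | Positive | Yes | No |
| RT-PCR, up to 3 days old | Negative | Yes | Yes |
| RT-PCR, up to 3 days old | Positive | Yes | **Yes** |

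Rows two and four carry the same evidence of infection at dosing, but only row two is excluded. SAP 3.3.2 takes the last non-missing pre-dose value as baseline, normally the Day 1 sample. A row-four child therefore also fails the SAP's own description of Cohort 1 as negative at baseline.

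**Step 2. Can a retained child count as a case?** The two documents differ.

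- SAP 4.2.4 determines incidence from AEs and makes any positive result indicating infection an AE, with no baseline condition. Protocol 8.1.1 also has none.
- Protocol 4.1 describes the AE as a post-baseline positive, with symptoms, in a child who was negative at baseline.

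A child infected on Day 1 could yield a post-dose positive through an unscheduled RT-PCR prompted by symptoms or, in non-neonates, through serology from Day 31 onward. Under SAP 4.2.4 that is a case. Under protocol 4.1 it is not, and the child sits only in the denominator.

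**Step 3. Size.** The plan states no figure to reproduce. SAP section 2 gives 46 participants in the FAS and none in Cohort 3, but no split between Cohorts 1 and 2. Assumed inputs:

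- n, the size of Cohort 1: 46 (the whole FAS, an upper bound), 31 (the protocol Table 5 minimum, 19 + 12, set for a trial of 100) or 20 (a smaller illustration)
- m, the number of retained Day 1-positive children: 1 or 3
- p, the incidence among Day 1-negative children: 10%

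Contribution of one counted child: 1/46 = 2.2, 1/31 = 3.2 and 1/20 = 5.0 percentage points.

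Reported incidence:

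- counted as cases: [p(n − m) + m]/n, a shift from p of (m/n)(1 − p)
- denominator only: p(n − m)/n, a shift from p of −p·m/n

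| n | m | Counted as cases | Denominator only | With the children removed |
|---|---|---|---|---|
| 46 | 1 | 12.0% | 9.8% | 10% |
| 31 | 1 | 12.9% | 9.7% | 10% |
| 20 | 1 | 14.5% | 9.5% | 10% |
| 46 | 3 | 15.9% | 9.3% | 10% |
| 31 | 3 | 18.7% | 9.0% | 10% |
| 20 | 3 | 23.5% | 8.5% | 10% |

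The direction of the error depends on which document's case rule is followed.

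**The case against.** **The effect may be nil.** No child in row four is documented. Cohort 1 also requires no COVID-19 symptoms in the 10 days before dosing and no known exposure, so such children may be few or absent. This stands as a limit on size. It does not justify the definition, since the protocol expressly foresees discordance for either entry test.

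**Protocol 4.1 already prevents miscounting.** If its baseline-negative condition governs, a retained child lowers incidence by 0.2 to 0.5 points at 10% (one child, n = 46 to 20). This stands in part. SAP 4.2.4, the text an analyst would program from, lacks the condition.

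**The classification meeting can deal with it.** SAP 4.1.1.1 provides for a documented, sponsor-approved decision on exclusions before database lock. That is discretionary, in an open-label study, and does not replace a stated rule.

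**A stronger reading to avoid.** A reader might infer that the mFAS wording also leaves misclassified children in the Cohort 2 results. The documents do not support this. SAP Table 2 assigns both "Change from baseline to Day 8 in viral load as measured by qRT-PCR" and progression to the SAF alone, so no mFAS wording changes either.

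Nor is a Cohort 2 child who is RT-PCR-negative on Day 1 shown to be uninfected. Criteria 10 and 11 require a recent positive test and a sign or symptom within 24 hours before Day 1, so one negative may reflect clearance or a sampling miss. For viral load, a child with no detectable virus at baseline has no log10 value unless one is imputed, and SAP 3.3.5 imputes nothing unless stated. Dilution of that summary is therefore not demonstrated.

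**Conclusion.** The mFAS is too narrow for its purpose. Followed exactly, it keeps any Cohort 1 child who entered on a negative RT-PCR up to 3 days old and was positive on Day 1 before dosing. The child always stays in the denominator and, under SAP 4.2.4, may also be a case.

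Each such child counted as a case contributes about 2 to 5 percentage points for an assumed Cohort 1 of 46 down to 20. The actual effect depends on the number of discordant children and the cohort split, neither of which the documents give. A reader should not take 2 to 5 points as an established bias, because it requires the SAP's case rule to prevail over protocol 4.1.

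The point concerns one secondary, descriptive endpoint and touches no primary analysis. It is still worth correcting, since the sensitivity analysis was added to answer exactly this question.

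**What to change.** 1. In SAP Table 1, define the mFAS as the FAS excluding every Cohort 1 participant with a positive Day 1 pre-dose central RT-PCR, whatever the screening test. Name that test in place of the undefined confirmatory test, and say how a missing Day 1 result is handled.
2. In SAP 4.2.4, count as incident only post-baseline positives in participants negative at baseline. Reconcile this with protocol 4.1 and 8.1.1, including how symptom-free infections found by serology fit the rule.
3. Report the number of Day 1-positive Cohort 1 children by entry test, so a reader can see whether the change matters.

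The cost is one line in Table 1, a sentence or two in 4.2.4 and one count. The Day 1 sample is already scheduled for every child, so no new data are needed.

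Optionally, the Cohort 2 viral-load and progression summaries could be repeated without children who were RT-PCR-negative on Day 1, with the SAF kept as the main analysis and the extra set named in SAP Table 2. That would be an added sensitivity analysis, not the correction of an error.

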## 2 CHANGES TO PROTOCOL PLANNED ANALYSES

A summary of adverse events by maximum intensity was planned in protocol Section 9.4.4. This was removed per AZD7442 program-level data presentation decision.

Enrolment into the study has been discontinued due to FDA feedback. No participant has been included for Cohort 3, and the full analysis set will contain 46 instead of 100 participants. Planned analyses for Cohorts with no participants will not be conducted.

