#### **4.2.3.2 ADA and nAb to AZD7442 in serum**

To evaluate the immunogenicity profile of AZD7442, the incidence of ADA and nAb to AZD7442 in serum will be assessed and summarized for the ADS (ie, ADS1 for AZD1061, ADS2 for AZD8895 and ADS3 for AZD7442).

The ADA for AZD7442 will be assessed for the individual agents AZD8895 and AZD1061 separately. The respective agent's ADA Evaluatable Analysis Set (see [Table 1: Analysis sets](#)) is to be used for the individual summary. The ADA titer of AZD7442 will be defined as the maximum of AZD8895 and AZD1061 titers at each time point.

Serum samples for AZD8895 and AZD1061 ADA assessments will be conducted utilizing a tiered approach (screen, confirm, titer), and ADA data will be collected at scheduled visits. The ADA results from each sample will be reported as either positive or negative. If the sample is positive in the confirmatory assay, the ADA titer will be reported as well. In addition, the presence of nAb will be tested for all ADA positive samples in the confirmatory assay. The nAb results will consist of a titer result and a subject status reported as positive or negative. Both of these results will be taken as received from the bioanalytical laboratory. A participant is defined as being ADA-positive if ADA evaluable and a positive ADA result in the confirmatory assay is available at any time, including baseline and all post-baseline measurements; otherwise the participant is defined as ADA negative if ADA evaluable.

Specifically for presentation of AZD7442, ADA-positive to AZD7442 is having a positive ADA result to AZD8895 and/or AZD1061 at any time, including baseline and all post-baseline measurements. ADA-negative is having negative ADA results to all evaluable AZD8895 and AZD1061 results at all time, including baseline and all post-baseline measurements. Summaries will include only ADA evaluable subjects for the respective agent.

In the evaluation of ADA results to AZD7442, if a component mAb (ieAZD8895 or AZD1061) is not ADA evaluable, all results from the component would be treated as missing.

ADA sample pos/neg status:

- For a sample of a particular visit, AZD7442 is + for that visit if either AZD1061 and/or AZD8895 is +

ADA subject pos/neg status:

- For a subject, AZD7442 is + if either AZD1061 and/or AZD8895 is + at any visit and if the subject is ADA evaluable for the mAb having the + result

Treatment-induced ADA+:

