- For AZD1061, ADA negative at baseline and ADA positive at  $\geq 1$  post-baseline assessments with ADA titer  $\geq 80$
- For AZD8895, ADA negative at baseline and ADA positive at  $\geq 1$  post-baseline assessments with ADA titer  $\geq 160$

- AZD7442 is treatment-induced ADA+ if either AZD8895 and/or AZD1061 is treatment-induced ADA+

Treatment-boosted ADA+:

- For AZD1061 or AZD8895, Baseline positive ADA titer that was boosted to  $\geq 4$  - fold during study period
- AZD7442 is treatment-boosted ADA+ if either AZD8895 and/or AZD1061 is treatment-boosted ADA+

Treatment-emergent ADA+:

- For AZD1061 or AZD8895, either treatment-induced ADA+ or treatment-boosted ADA+
- AZD7442 is treatment- emergent ADA+ if either AZD8895 and/or AZD1061 is treatment- emergent ADA+

Persistently ADA+:

- For AZD1061, participants who are Treatment-emergent ADA positive, and having ADA post-baseline positive with ADA titer  $\geq 80$  at  $\geq 2$  post-baseline assessments (with  $\geq 16$  weeks between first and last positive) or positive with ADA titer  $\geq 80$  at last post-baseline assessment
- For AZD8895, participants who are Treatment-emergent ADA positive, and having ADA post-baseline positive with ADA titer  $\geq 160$  at  $\geq 2$  post-baseline assessments (with  $\geq 16$  weeks between first and last positive) or positive with ADA titer  $\geq 160$  at last post-baseline assessment
- AZD7442 is persistently ADA+ if either AZD8895 and/or AZD1061 is persistently ADA+

Transiently ADA+

- For AZD1061, participants who are Treatment-emergent ADA positive, and having at least one post-baseline ADA positive assessment with titer  $\geq 80$  and not fulfilling the conditions of persistently positive
- For AZD8895, participants who are Treatment-emergent ADA positive, and having at least one post-baseline ADA positive assessment with titer  $\geq 160$  and not fulfilling the conditions of persistently positive
- For AZD7442, treatment-emergent ADA positive and not fulfilling the conditions of persistently positive.

The number and percentage of AZD7442, AZD8895 and AZD1061 ADA-evaluable positive/negative participants in each cohort will be determined. The number of ADA-

evaluable participants in the cohort will be used as the denominator for percentage calculation.

To evaluate the ADA responses to AZD7442, AZD8895 and AZD1061 in serum the following analyses will be presented:

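### The AZD7442 ADA rule can call a child negative on one antibody alone, even when a confirmed positive on the other has been set to missing

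*SAP*

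**What the plan says.** SAP Table 1 defines three ADA sets. ADS1 (AZD1061) requires a "non-missing baseline AZD1061 ADA result and at least one non-missing post-baseline AZD1061 ADA result", and ADS2 (AZD8895) is worded the same way. ADS3, for the combination AZD7442, is the union of the two: "All participants who are AZD8895 ADA evaluable and/or AZD1061 ADA evaluable". Protocol Table 17 uses the same union.

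SAP 4.2.3.2 then gives several rules for AZD7442 status:

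- General positive definition: "ADA-positive to AZD7442 is having a positive ADA result to AZD8895 and/or AZD1061 at any time", with baseline results included. It carries no component-level evaluability condition.
- Negative definition: "ADA-negative is having negative ADA results to all evaluable AZD8895 and AZD1061 results at all time".
- Sample-level rule: a visit is positive if either antibody is positive. Again there is no evaluability condition.
- Subject-level rule: a positive on either antibody counts only "if the subject is ADA evaluable for the mAb having the + result".
- Non-evaluable component: if a component "is not ADA evaluable, all results from the component would be treated as missing".
- Denominator: the ADA-"evaluable participants in the cohort will be used as the denominator for percentage calculation".

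The section also asks for spaghetti plots of PK concentration and nAb titre over time, with lines distinguished by ADA subject status.

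**The concern.** AZD7442 is positive if either antibody is positive. A negative is therefore established only when both antibodies have been assessed and both are negative. ADS3 does not require that, and the negative rule looks only at evaluable results. Two kinds of children are then labelled AZD7442 ADA-negative without support: those with no usable information on one antibody, and those with a confirmed positive on an antibody for which the baseline, or every post-baseline result, is missing.

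The second kind is the more serious, because a result the laboratory confirmed is removed and the child is reported as its opposite. Incidence of ADA to AZD7442 is a secondary endpoint in all cohorts. The same status separates the lines in the plots meant to show whether ADA affects PK or nAb titre, so such a child would be drawn among the negatives.

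**Working it through.** **No figure to reproduce.** The documents give no ADA incidence, no size for ADS3 and no number of children evaluable for one antibody only. The one usable number is the bound from SAP Section 2: "the full analysis set will contain 46 instead of 100 participants". ADS3 therefore holds at most 46 children.

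**Direction.** Apply the subject-level rule to every combination of evaluability (at least one antibody) and confirmed status. That is 3 evaluability patterns × 4 result patterns = 12 cases. Compare the outcome with the general definition, under which any confirmed positive on either antibody counts.

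| Evaluable for | AZD1061 result | AZD8895 result | Status under rule | Any confirmed positive |
|---|---|---|---|---|
| both | all four patterns | all four patterns | agrees | agrees |
| AZD1061 only | negative | positive | **negative** | **positive** |
| AZD1061 only | other three patterns | other three patterns | agrees | agrees |
| AZD8895 only | positive | negative | **negative** | **positive** |
| AZD8895 only | other three patterns | other three patterns | agrees | agrees |

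Two of the 12 cases differ. Both turn a confirmed positive into a negative, and none goes the other way. A positive on the evaluable antibody still counts.

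**Size.** Let N be the number in ADS3, k the positives under the rule, and m the children with a discarded positive. Only N ≤ 46 comes from the documents; k and m are assumptions.

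- Rule: k/N
- Discarded positives counted: (k + m)/N
- Those children left out: k/(N − m)

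With N = 46 and k = 5, the rule gives 5/46 = 10.9%.

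| m | counted | left out |
|---|---|---|
| 0 | 10.9% | 10.9% |
| 1 | 6/46 = 13.0% | 5/45 = 11.1% |
| 2 | 7/46 = 15.2% | 5/44 = 11.4% |
| 3 | 8/46 = 17.4% | 5/43 = 11.6% |

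Compared with counting the positive, each affected child costs 1/N: 2.2 points at N = 46, 2.5 at 40 and 3.3 at 30. Compared with leaving the child out, the difference for one child at N = 46 and k = 5 is about 0.2 points.

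**Which denominator is safe.** Suppose each antibody has ADA rate p, independently, and a share f of ADS3 is evaluable for one antibody only, unrelated to ADA status. The true combination rate is 1 − (1 − p)². For illustration take p = 8%, which gives 1 − 0.92² = 15.4%. Three ways of handling the single-component children:

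- Present rule: (1 − f)(0.1536) + f(0.08)
- Keep single-component positives, drop single-component negatives: [(1 − f)(0.1536) + f(0.08)] / [(1 − f) + f(0.08)]
- Children evaluable for both only: 0.1536 whatever f is

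| f | present rule | keep positives, drop negatives | both evaluable |
|---|---|---|---|
| 0.1 | 14.6% | 16.1% | 15.4% |
| 0.2 | 13.9% | 17.0% | 15.4% |
| 0.3 | 13.2% | 18.2% | 15.4% |

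The values of p and f are not in the documents and are not a forecast. The table shows only that a denominator whose membership depends on the result is biased upward, while one that depends on evaluability alone is not, under these assumptions.

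**The case against.** The strongest objection is that the situation may never arise. Protocol Table 3 schedules a single serum sample for ADA at each visit. The blood-volume hierarchy in Protocol 8.5.1 puts ADA last, and a reader might infer from this that incomplete component data are foreseeable and that the combination incidence is therefore biased low. The documents do not support that step. A draw given up for lack of blood loses both antibodies at that visit. A child who loses the baseline, or every post-dose sample, in that way belongs to none of ADS1, ADS2 and ADS3. Evaluability for one antibody only needs one assay to fail or go unreported on a shared sample. Nothing in the documents says how often that happens. This part of the objection stands.

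The rule is also explicit, prespecified and descriptive. SAP 4.1.1.2 lists each child's analysis sets and tabulates set sizes, so a difference between ADS1, ADS2 and ADS3 would show. ADA results are listed by participant and time point, and component-level incidence is reported on ADS1 and ADS2. These features make the problem detectable, but they do not correct the AZD7442 table or the plots.

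Finally, the misclassification applies to ADA-positive at any time. For the treatment-induced and treatment-boosted categories, a positive with no baseline, or a baseline positive with no later result, cannot be classified. That supports a not-determinable class; it does not support calling the child negative.

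**Conclusion.** The point holds as a fault in the status rule. SAP 4.2.3.2 can report a child with a confirmed positive on one antibody as AZD7442 ADA-negative, against the general definition in the same section, and can give the same label to a child for whom only one antibody was assessable. Any resulting error in combination incidence is downward.

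It does not hold as a claim that the incidence will be biased by a known amount. The number of affected children is not stated; if ADS1, ADS2 and ADS3 are the same children, the bias is zero. The figure of at least 2.2 points per child rests on N ≤ 46 and on counting the discarded positive. Leaving the child out moves the estimate far less. The correction is worth making because the error runs one way, touches a secondary endpoint and is cheap to remove.

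**What to change.** - Base AZD7442 ADA incidence, and the ADA-negative group in the PK and nAb plots, on children evaluable for both antibodies, whatever their result.
- Report children evaluable for one antibody only as a separate not-determinable count, broken down by the evaluable component's result and by whether a confirmed positive on the other component was discarded.
- Add a sensitivity summary in which any confirmed positive on either antibody makes the child AZD7442-positive at any time.
- Align the general, sample-level and subject-level definitions in SAP 4.2.3.2, so that one child cannot be positive under one and negative under another.
- Leave ADS1 and ADS2 unchanged. Because Protocol Table 17 carries the same union, record the change in SAP Section 2.

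Keeping single-component positives while dropping single-component negatives should be avoided, for the reason shown in the working.

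The cost is wording in Table 1 and 4.2.3.2, one derivation flag and one extra summary. The downside is that a few children, including any whose only evaluable component is positive, leave the main AZD7442 denominator. The main estimate can then fall as well as rise. For example, take 5 positives among 46, with two children evaluable for one antibody only. If one of the two is among the five positives and the other has a discarded positive, the both-evaluable figure is 4/44 = 9.1%, and the sensitivity summary gives 6/46 = 13.0%. Showing both, with the not-determinable count, lets the reader see the range.
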